Subjects will receive HD Analyzer measurements of the OSI (ocular surface index) at enrollment, 1 month, and 3 month timepoints per manufacturer instructions.

XVI. Safety and Data Monitoring

a. Adverse Events

All adverse events will be recorded and reported via the Adverse Event Reporting Form (AERF, MOP), and entered into an Adverse Event Log for the patient (MOP). Below is a list of adverse events (AE) and serious adverse events (SAE).

Ocular Adverse Event	Non-Serious	Serious
Ocular Irritation	Mild to moderate irritation treatable with adjuvant lubricant drops.	Impairs patient's ability to complete activities of daily living, after normal surgical recovery period.
Ocular Hypertension	≥ 24 mm Hg	Surgery required (laser or incisional)
Subconjunctival hemorrhage	Subconjunctival hemorrhage greater than 5mm indiameter after injection	
Cataract	Visually significant cataract, cataract surgery indicated	
Infectious scleritis or keratitis		Any occurrence is a serious adverse event
Corneal or scleral perforation		Any occurrence is a serious adverse event

Systemic Adverse Event	Non-Serious	Serious
Nausea	Any nausea	Severe discomfort, minimal food intake for 3 or more days or at least a 2.5 kg weight loss resulting from nausea
Vomiting	Any vomiting	Severe: vomiting all food or fluids in 24 hours or orthostatic hypotension or at least a 2.5 kg weight loss resulting from vomiting
Diarrhea	Any diarrhea	Severe, bloody diarrhea or 8-9 loose stools in 24 hours or orthostatic hypotension or at least a 2.5 kg weight loss resulting from diarrhea
Dyspnea	Breathlessness on significant exertion or breathlessness at normal level of activity	Breathlessness at rest
Headache	Moderate, non-narcotic analgesic therapy required	Severe, requires narcotic therapy
Fatigue	Self-reported fatigue	Normal activity reduced >50%; cannot work or unable to care for self
Fever for 12 hours	> 100.6 to 103°F/39.5°C	≥ 103°F/39.5°C
Muscle strength	Subjective weakness, no objective symptoms or mild objective weakness, no decrease in function	Objective weakness, function limited, or worse

Mood	Self-reported mood changes or psychiatric diagnosis not requiring medical therapy (specify):	Psychiatric diagnosis requiring medical treatment or hospitalization

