Cardiac function	Mild congestive heart failure (CHF) or arrhythmia not requiring treatment or moderate CHF or worse, arrhythmia requiring treatment, stable angina	Unstable angina, severe CHF, myocardial infarction, or arrhythmia requiring hospitalization
Neurologic function	Numbness or tingling	Total loss sensation
Allergic reaction*	Pruritis without rash or erythema or localized urticaria, diffuse maculopapular rash, dry desquamation	Generalized urticaria, angioedema or worse, vesiculation, moist desquamation, ulceration up to and including: exfoliative dermatitis; mucous membrane involvement; or Stevens-Johnson Syndrome, or erythema multiforme, or necrosis requiring surgery
Systemic infection	Any systemic infection.	Systemic infection requiring hospitalization.
Other systemic	No treatment required and no limitations or mild impairment of usual activities	Vigorous treatment, hospitalization usually required, immediate risk of death
Seizure		Any occurrence is a serious adverse event
Cancer		Any occurrence is a serious adverse event
Congenital Anomaly/Birth Defect		Any occurrence is a serious adverse event
Disability or Permanent Damage		Any occurrence is a serious adverse event
Hospitalization		Any occurrence is a serious adverse event
Life-threatening event		Any occurrence is a serious adverse event

Serious adverse event collection begins after the patient has signed informed consent and has undergone pterygium excision. If a patient experiences an SAE after signing informed consent, but prior to undergoing surgery, the event will be treated as unrelated to the study unless the investigator feels the event may have been caused by a protocol procedure. Adverse events (SAEs) occurring after a patient has received the last injection of the study drug will be collected for 30 days after the last dose of study drug, regardless of the investigator's opinion of causation. Thereafter, SAEs are not required to be reported unless the investigator feels the events were related to the study drug or a protocol procedure.

b. Adverse Event Reporting

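### SAE collection in XVI.a starts only after a pterygium excision that this oral-drug trial does not include, and the linked unrelated-by-default rule has no defined scope and conflicts with XVI.c on two of its three readings

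*Combined protocol and SAP*

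**What the plan says.** Study Design (iii) describes a randomised, masked comparison of oral azithromycin with placebo, taken weekly for 3 weeks, with warm compresses. The Schedule of Procedures (XIII) lists an initial visit, a 1 month visit and a 3 month visit (days 76-96), and no operation or injection.

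The paragraph below the adverse event tables in XVI.a sets four rules:

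- **Start:** "Serious adverse event collection begins after the patient has signed informed consent and has undergone pterygium excision".
- **Default causality:** "the event will be treated as unrelated to the study unless the investigator feels the event may have been caused by a protocol procedure". The period to which this default applies is given as "after signing informed consent, but prior to undergoing surgery".
- **End window:** events "occurring after a patient has received the last injection of the study drug" are collected for 30 days after the last dose of study drug, whatever the investigator thinks of causation.
- **After the window:** "Thereafter, SAEs are not required to be reported unless the investigator feels the events were related to the study drug or a protocol procedure".

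Other text in the same part of the protocol carries no surgical condition:

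- XVI.a opens with "All adverse events will be recorded and reported via the Adverse Event Reporting Form".
- XVI.b requires an alert to the medical monitor within 24 hours for any SAE. It also requires a report to the human research committee within 5 working days for serious or unexpected events judged definitely, probably or possibly related.
- XVI.c gives causality to the investigators and the monitoring board. It reserves the unrelated category for events whose cause is known, and requires any uncertainty to be graded possibly related and reported.
- XVI.e ties follow-up to relatedness, both for unresolved treatment-related events and for SAEs related to study drug or trial procedures.

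**The concern.** The SAE paragraph is the only place that defines when SAE collection starts and stops, and its start condition is an operation that nobody has in this trial. The default rule depends on the same missing operation, so its scope cannot be read off the page. Its exception covers a suspected protocol procedure but does not name the study drug, although the last sentence of the paragraph lists the two separately.

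At stake is consistent handling of SAEs. Relatedness decides whether the 5-working-day committee report is due and whether the follow-up duties in XVI.e apply. If XVI.a and XVI.c grade the same event differently, staff who each follow the protocol can act differently.

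**Working it through.** There is no stated statistical figure to reproduce. The check is a count, a comparison of the rules, and one date calculation.

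**1. Can the start condition be met?** Study Sizing (IX) plans 19 patients per arm: 2 × 19 = 38. Neither the design, the non-medication intervention nor the schedule contains an excision, other surgery or an injection. Patients who can meet the condition through protocol procedures: 0 of 38.

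**2. Is this one stray word?** XVI.a contains eight references to surgery or injection.

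- Five are leftovers. Three are in the SAE paragraph: the pterygium excision, the pre-surgery period and the last injection. Two are in the ocular table: the serious grade of irritation ("activities of daily living, after normal surgical recovery period") and the post-injection condition for subconjunctival haemorrhage.
- Three are ordinary descriptions of an event or its treatment: surgery for ocular hypertension, an indication for cataract surgery, and "necrosis requiring surgery" under allergic reaction.
- 5 + 3 = 8.

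**3. What does the default cover?** Take an SAE of uncertain cause for which the investigator does not suspect a protocol procedure.

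| Reading of surgery | Period covered by the default | Grade under XVI.a | Grade under XVI.c | Conflict |
|---|---|---|---|---|
| A. Literal; it never happens, so every patient stays in the pre-surgery period | All time after consent, no end | Unrelated | Possibly related, reported | Yes, including events on study drug |
| B. It stands for start of study treatment | Consent to first dose | Unrelated | Possibly related, reported | Yes, for pre-dose events only |
| C. It has no referent, so the default never applies | None | No default | Possibly related, reported | No |

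The start condition in step 1 fails on all three unless the words are replaced.

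**4. What happens at the end of the window?** The window can be calculated, because the sentence that mentions an injection also counts 30 days from the last dose. Assume weekly doses on days 0, 7 and 14, with day 0 the initial visit:

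- End of window: 14 + 30 = day 44.
- Gap to the 3 month visit: 76 − 44 = 32 days to 96 − 44 = 52 days.
- If the first dose falls *d* days after the initial visit, the window ends at day 44 + *d* and the gap is 32 − *d* to 52 − *d* days.

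During that gap the after-window sentence asks only for SAEs the investigator thinks related, while the general rules in XVI.a and XVI.b ask for all of them.

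**The case against.** Four arguments on the other side deserve weight.

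- **The safety net is intact.** A reader might infer that SAEs would go uncollected. The documents do not support that: the general recording rule, the 24-hour alert and the monitoring committee's review (XVI.f) carry no surgical condition, and XVI.b says reporting follows the human research committee's guidelines. This stands. But those rules do not repair the SAE paragraph; they disagree with it about when collection starts.
- **Reading A is strained.** A reader might infer that every SAE on azithromycin is classed as unrelated. XVI.c, XVI.e and XVII.a all presuppose that SAEs on study drug are assessed individually, so that is not what the protocol as a whole intends. This stands too. Reading B is the more natural one: leaving the drug out of the exception makes sense if no drug has yet been given. Yet B still leaves a conflict with XVI.c, confined to pre-dose SAEs of uncertain cause.
- **The end window works.** It is anchored to the last dose, which does occur, so the reference to an injection is wrong wording and not a missing endpoint. This is correct.
- **The after-window sentence may be a deliberate, specific limit on the general rules.** It may be, and related events stay reportable under it. The documents do not say so, which makes this an ambiguity to clarify and not a proven contradiction.

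Dismissing the paragraph as obvious leftover text does not settle the matter. Staff would still have to guess the replacement start point and whether the default survives.

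**Conclusion.** The point holds, and the text must be corrected. The start condition for SAE collection cannot be met by any of the 38 planned patients through protocol procedures and disagrees with the unconditional rules elsewhere in XVI. The scope of the unrelated-by-default rule is undefined. On two of three readings it can give an SAE of uncertain cause a different grade from XVI.c, with consequences for the 5-working-day report and for follow-up under XVI.e. On the more natural of those two readings, the conflict is limited to the interval from consent to first dose.

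Capture and attribution are therefore inconsistent, not absent. The documents give no SAE rate, so the number of events that would be handled differently cannot be estimated. The primary outcome, power and alpha are unaffected. The gap of about 32-52 days before the 3 month visit rests on the assumed dosing days 0, 7 and 14. The Manual of Procedures was not available and might already settle some of this.

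**What to change.** In XVI.a:

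1. Replace the surgical start condition with a start point that exists in this trial and agrees with the general recording rule in XVI.a and the alert rule in XVI.b.
2. Delete the unrelated-by-default sentence, so that XVI.c alone governs causality.
3. Reconcile the reference to a last injection with the last dose of study drug named in the same sentence.
4. Reconcile the two leftover table conditions (surgical recovery under irritation, injection under subconjunctival haemorrhage) with an oral regimen. The other three references to surgery in the tables can stay.
5. State whether the after-window sentence limits the general rules in the period up to the 3 month visit.

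The cost is wording: the SAE paragraph and two table cells, plus a check of the Manual of Procedures forms for the same leftovers. No new visits are needed. There is one small downside: if the unconditional rules are kept, mandatory SAE reporting runs longer than the after-window sentence now requires, by about 32-52 days up to the 3 month visit under the dosing days assumed above.

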For microbiome outcomes, the alpha diversity (local species pool) of the population will be analyzed and compared pre-and post-treatment within and between the azithromycin and control groups. The difference between the bacterial microbiome in the azithromycin and placebo arm will be assessed using a PERMANOVA with an L^2 norm distance measure. Secondary analyses will include L^1 and L^0 norms, as well as a phylogenetic distance. In addition, we will assess whether bacterial alpha diversity is decreased in the antibiotic treated arm with the primary outcome being the Simpson's index (L^2), with secondary analyses assessing Shannon's (L^1) and Richness (L^0).

IX. Study Sizing

The number of patients was calculated by assuming a 20% difference in Ocular Surface Disease Index (OSDI)²⁴ score at the primary outcome between treatment and placebo groups, with 80% power and a significance level of 0.05. This yielded a total of 16 patients per arm. To account for loss to follow up, a total of 19 patients per arm will be recruited.

X. Placebo

The oral azithromycin placebo will be a sugar pill, and will be made by the UCSF Investigational Pharmacy.

XI. Non-Medication Intervention

All patients will receive education regarding non-medication interventions for their Meibomian gland disease. This will be instruction to perform warm compresses over both eyes for 10 minutes twice per day. The handout that will be given to patients is available in the Manual of Procedures (MOP).

XII. Masking

The UCSF Investigational pharmacy will perform randomization according to randomization schedule. All masking of investigational medications will be performed by the UCSF Investigational Pharmacy.

Azithromycin tablets will be over-encapsulated for masking purposes to match the placebo pills. Artificial tears will be used as the placebo for dexamethasone, and both will be in identical eye dropper vials.

Both patients and physicians will be masked as to study assignment. The clinical coordinator and the Investigational Pharmacy will have access to the randomization key.

XIII. Schedule of Procedures

The initial visit will be at enrollment. The 1 month visit will be 21-35 days after the initial visit, and the 3 month visit will be 76-96 days after the initial visit.

Procedure	Initial	1 Month	3 Months
Visual Acuity	X	X	X
Refraction	X		
IOP	X	X	X
Schirmer's	X	X	X
TBUT	X	X	X
MGE	X	X	X
SICCA Score	X	X	X
NSPI-E	X	X	X
DEQ-5	X	X	X
OSDI	X	X	X
PHQ-9	X		

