Principal investigator: [name].

Email: [contact]

[contact]

e. Investigator Follow-Up:

The investigator will follow all unresolved treatment-related adverse event until the event has resolved to baseline grade or better, the event is assessed as stable by the investigator, new therapy is initiated, the patient is lost to follow-up, or the patient withdraws consent. Every effort will be made to follow all serious adverse events considered to be related to study drug or trial-related procedures until a final outcome can be reported.

During the study period, resolution of adverse events (with dates) should be documented on the patient's Adverse Event Log (MOP) and in the patient's medical record to facilitate source data verification. If, after follow- up, return to baseline status or stabilization cannot be established, an explanation will be recorded on the patient's Adverse Event Log.

f. Data Review

The DSMC will review of data from enrolled patients at bi-annual committee meetings. The discussion will include the number of patients and any significant adverse events. If necessary, the Study Coordinator will provide unmasked treatment assignment to the committee.

g. Interim Analysis

Interim analyses of efficacy are not planned for this study.

h. Early Stopping of the Study

Stopping for harm will be done at the judgment of the DSMC.

Committee

[name] ([contact])

[name] ([contact])

i. Loss to Follow up

All patients will be offered enrollment in the text-messaging appointment reminder service. Patients that do not show up for scheduled study visits will be contacted by the study coordinator the day following their visit via phone and offered rescheduling. If they are unable to be contacted that day, repeated attempts will be made weekly for 4 weeks to contact patients lost to follow up. Additional attempts will be made at the 6- and 12-month points.

XVII. TREATMENT STOPPING RULES

a. Discontinuation:

Patients who discontinue one of the study treatments due to intolerance or side effects will be observed to the end of the study period unless they are unwilling or unable to return.

In addition, the investigator will discontinue patients from the study drug in the following circumstances:

- The investigator decides that the patient should be withdrawn from the study. If a SAE occurs and the investigator deems stopping study therapy is necessary, the investigator will discontinue the study therapy and take appropriate measures.

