- The patient or attending physician requests withdrawal of the patient from the study.
- The investigator or the study sponsor stops the study or stops the patient's participation in the study for medical, safety, regulatory, or other reasons consistent with applicable laws, regulations, and good clinical practice (GCP).
- The patient becomes pregnant or fails to use adequate birth control (for women with reproductive potential).
- The patient is noncompliant with study procedures.

When a subject withdraws before completing the study, the reason for withdrawal is to be documented in the Patient Dropout Form (MOP).

Study agents assigned to the withdrawn subject may not be assigned to another subject. Subjects who withdraw will not be replaced.

References

1. Pflugfelder SC. Prevalence, burden, and pharmacoeconomics of dry eye disease. The American journal of managed care 2008;14:S102-6.
2. The epidemiology of dry eye disease: report of the Epidemiology Subcommittee of the International Dry Eye WorkShop (2007). The ocular surface 2007;5:93-107.

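### Study drug must be stopped for pregnancy or inadequate contraception, but the protocol text neither excludes nor checks for either before dosing

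*Combined protocol and SAP*

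**What the plan says.** Section XVII.a makes stopping mandatory: "the investigator will discontinue patients from the study drug in the following circumstances". The triggers include "The patient becomes pregnant or fails to use adequate birth control", limited to women who could become pregnant, and "The patient is noncompliant with study procedures". The same section keeps some stopped patients under observation: "Patients who discontinue one of the study treatments due to intolerance or side effects will be observed to the end of the study period". Those who will not or cannot return are excepted. It gives no equivalent statement for the other triggers.

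Section iii sets the dose at 1 gram weekly for three weeks. Section XIII schedules three visits: enrollment, days 21-35 and days 76-96. Section V lists 3 inclusion and 13 exclusion criteria, and none concerns pregnancy or contraception.

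Outside these visits, XVI.i offers optional appointment-reminder texts and a follow-up call for absentees: "Patients that do not show up for scheduled study visits will be contacted by the study coordinator the day following their visit".

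**The concern.** The protocol treats pregnancy and inadequate contraception as reasons why a patient must not go on taking study drug. Yet a woman who is pregnant or not using contraception at entry meets no exclusion, is asked no named question, and can be given the full course. The rule then depends on her knowing of the pregnancy and volunteering it. What is at stake is a safety stop that the protocol itself requires.

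A second, smaller gap lies beside it. The text names no record of doses taken. If the OSDI or microbiome comparison is null, readers will ask whether azithromycin failed or was not taken. Intake that is not recorded at the time is hard to recover later.

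**Working it through.** **Step 1. Where a check could stand.**

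| Place in the protocol | What it holds | Pregnancy or contraception check? | Record of doses taken? |
|---|---|---|---|
| V, criteria | 3 inclusion, 13 exclusion items | No | Not applicable |
| XIII, table | 11 procedures (vision, eye examination, questionnaires) | No | No |
| XVI.a, adverse events | Birth defect as a serious event: an outcome, not a check | No | No |
| XVI.i, loss to follow-up | Optional visit reminders; calls after a missed visit, so day 22 at the earliest | No | No |
| XVII.a, dropout form | Reason for withdrawal | No | No |
| Manual of Procedures items named in the text | Adverse event form and log, serious event form, dropout form, compress handout | No | No |

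Absence from the XIII table alone proves little, because the table is incomplete. Section XV.5 says "Subjects will receive HD Analyzer measurements of the OSI (ocular surface index) at enrollment, 1 month, and 3 month timepoints", and the table omits that too. The finding rests on the fact that no other section supplies the check either.

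**Step 2. Timing.** The protocol does not state the first-dose day; call it *s*. Doses fall on days *s*, *s* + 7 and *s* + 14. All three are due before a 1-month visit on day *v* when *s* + 14 < *v*.

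- Earliest visit, *v* = 21: *s* < 7, so starts on days 0-6.
- Latest visit, *v* = 35: *s* < 21, so starts on days 0-20.

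| First dose | Dose days | Doses due before day 21 | Doses due before day 35 |
|---|---|---|---|
| Day 0 | 0, 7, 14 | 3 | 3 |
| Day 6 | 6, 13, 20 | 3 | 3 |
| Day 7 | 7, 14, 21 | 2 (third due on day 21) | 3 |
| Day 8 | 8, 15, 22 | 2 | 3 |
| Day 21 | 21, 28, 35 | 0 | 2 (third due on day 35) |

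**Step 3. What each scheduled contact can prevent.** For starts on days 0-6, a check at the initial visit before dispensing can withhold 3 of 3 doses. A check at the 1-month visit can withhold 0 of 3, if doses are taken when due.

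**Step 4. The dose record.** Section IX plans 19 patients per arm: 19 × 3 = 57 azithromycin doses, and 38 × 3 = 114 doses in all. With starts on days 0-6 the last dose falls on days 14-20.

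- Asked at the 1-month visit, recall covers 21 − 20 = 1 to 35 − 14 = 21 days.
- Asked first at 3 months, it covers 76 − 20 = 56 to 96 − 14 = 82 days.

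The 1-month visit is therefore the better place to ask.

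**The case against.** The strongest reply is that much may sit outside the text. The Manual of Procedures may hold a dose log or a pregnancy procedure, and the consent pages, which were not available, may carry contraception instructions. This stands as a limit: the finding concerns the protocol text only.

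A second reply is that the trigger may be inherited. Section XVI.a refers to a patient who "has received the last injection of the study drug will be collected for 30 days after the last dose of study drug", and to pterygium excision, although this trial gives capsules. That is plausible, and it changes the remedy: the sponsor should first decide whether the trigger belongs. The documents state no pregnancy risk from the drug. But while the rule stands, criteria and entry procedures should match it.

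A reader might infer more than the documents support:

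- *That no scheduled contact precedes dosing.* The initial visit does. The gap is that no check is named there.
- *That the rule cannot work during treatment.* A patient may report a pregnancy at any time, and a start on day 8 or later with a day-21 visit leaves a dose to withhold.
- *That the noncompliance trigger fails in the same way.* It refers to study procedures, a term that XIII and XV use for visits and eye examinations, so it need not mean drug intake. Missed visits do prompt a call. A patient who is not taking drug needs no safety stop.
- *That checks between doses are needed.* First to last dose spans 14 days, so such a question would mainly find a pregnancy that the patient already knows of. Because "The clinical coordinator and the Investigational Pharmacy will have access to the randomization key", calls by that coordinator would be unsuitable, and the protocol names no masked contact role.
- *That the serious-event window is materially harmed by an unknown last-dose date.* Section XVI.a keeps related events reportable after the window closes, and XVI.c treats uncertain causality as possibly related.

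**Conclusion.** The concern holds in a limited form. The protocol requires drug to be stopped for pregnancy or inadequate contraception, but as written it can enroll and fully dose a patient to whom that rule applies. For starts on days 0-6, the initial visit is the one scheduled contact at which the rule can reliably act, and no check is named there. The missing dose record is a secondary point about interpretation. It leaves the comparison of assigned groups valid, and the documents do not suggest otherwise.

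The size in patients cannot be given. The documents state neither how many participants could become pregnant nor a missed-dose rate. The timing rests on an early first dose, which is an assumption. The change is worth making because it is cheap and serves safety. Confidence is medium, because the Manual of Procedures and consent pages could not be seen.

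**What to change.** 1. **Section V:** add an exclusion for pregnancy or inadequate contraception in women who could become pregnant. If the sponsor judges the XVII.a trigger to be carry-over from another protocol, delete the trigger instead.
2. **Initial visit, XIII:** if the trigger stays, ask about both before drug is dispensed, and tell patients to report a pregnancy before taking any further dose. The sponsor's clinicians decide whether a test is also needed.
3. **1-month visit, XIII:** add a capsule count and self-reported dose dates, or cite the Manual of Procedures log if one exists.
4. **XVII.a:** state that patients stopped under any trigger stay in follow-up and are analyzed in their assigned group. The present wording covers only intolerance and side effects.

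The cost is a few minutes at two existing visits and a few sentences of text. A few patients may be excluded. Counts and self-report can overstate intake, so the record helps in reading a null result but does not settle its cause.
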